4.7. Monitoring of Study Progress (see also Table 1 in 4.4.)

Accrual, retention. Review of the number of screened and eligible participants/month, accrual rates, adherence to inclusion/exclusion criteria will occur weekly. This will help evaluate the adequacy of the eligibility criteria and of the recruitment procedures and to address concerns in a timely fashion.

Compliance with the intervention protocol. Protocol compliance will be assessed in an ongoing fashion. Participants' compliance will be monitored by the instructors and PD and will involve tracking of the number of session attended and of the total time of individual mindfulness practice. Instructors' compliance will be supervised by [name] according to the Treatment Fidelity Workgroup guidelines. At the end of each intervention session the instructor will complete a checklist in which duration and delivery of the intervention as specified in the intervention script will be evaluated, as well as the patient's level of engagement during the session. In order to monitor the consistency of the delivery of the intervention, each session will be digitally recorded. Ten percent of all recorded sessions will be randomly reviewed.

Data accuracy. The PD and data manager , in collaboration with the data analyst, will be responsible for tracking participants to ensure that all data are collected in a timely and efficient fashion; for developing and generating monitoring reports; for providing timely and relevant feedback to project staff and leadership regarding the accuracy and precision of data. The following data verification procedures are planned:

Research Electronic Data capture (REDCap) technology will be used for direct data entry during the interviews. REDCap employs automatic checks for values that are out of range or represent errors of logic. Outliers will be corrected with verification from participants.

Calculations (i.e., from self-report measures, when necessary) will be independently performed by two different persons and any invalid score (i.e. scores that differ between the two people) will be recalculated.

5. ELIGIBILITY

5.1. Population

This study will enroll 50 *HIV+* adult outpatients (25 per condition). The sample will be representative of the demography of the HIV epidemic and of the clinic outpatient population ($n = 1614$ outpatients with 70% male and 30% female; 60% White, 30% African American; 10% other/mixed; 25% Hispanic). We expect no difficulties recruiting 50 patients for this research.

5.2. Participant Source

Participants will be recruited from the Immunology Clinic (IC) at The Miriam Hospital (TMH) in Providence, RI. The Immunology Center is an urban HIV-clinic that provides comprehensive primary and specialty care for over 1,600 HIV-infected patients. It is the largest HIV clinic in Rhode Island with patients also referred from western Connecticut and southern Massachusetts. An average of 300-400 HIV-infected patients are seen in the clinic per month.

The Immunology Center is located at [name]. The clinic occupies the first floor. The second floor, designed to support clinical research, has exam and interview rooms dedicated to clinical research. Co-I [name], who is also a clinic treatment provider, will act as a liaison between the study and the clinic.

Vulnerable populations. This study will not recruit individuals from the traditionally vulnerable populations (i.e., adults unable to consent, infants, children, teenagers or pregnant women). However, the PIs and the research team recognize that HIV-infected persons are vulnerable because of their disease status and because the disease disproportionately affects individuals with a range of vulnerability characteristics—including racial/ethnic minorities, women, and/or injecting drug users—not necessarily specified in the current definition and categories. Therefore, we will uphold the highest standards to protect study participants.

An overriding concern in HIV research is confidentiality and privacy because breaches of confidentiality could have adverse consequences. Therefore, as described in this protocol (and in our research application and other study communications), we will establish procedures that ensure that our study guards and protects participants' confidentiality. We will adopt standard protections, including as the following: (a) where identifiers are not required, they will not be recorded; (b) if identifiers are recorded, they will be separated, to the greatest extent possible, from data and securely stored, with linkage restored only if necessary to conduct the research; (c) potential participants will be given a fair and clear explanation of how information about them will be handled, including whether and how the information will be recorded in their medical records; (d) we will seek and obtain a Federal Certificate of Confidentiality so that we can resist attempts to force disclosure of participants' research records; and (e) information that is recorded (e.g., focus group discussions) will have all identifying information removed from transcripts, and the source materials will be destroyed once transcripts are prepared and checked for accuracy.

Assessments for Study 4 will be collected at baseline, at completion of intervention sessions (post-intervention), and approximately 3 months after completion of intervention sessions (3 month follow-up). In addition, we will conduct monthly telephone calls for the unannounced pill counts, to be used as a measure of medication adherence. The entire duration of the study is projected to be 2 years. Each individual will be involved for about 6 months from enrollment with the maximum individual involvement to be 7.5 months in cases where the participant's intervention start date is delayed due to extenuating circumstances (e.g., death in the family or hospitalization).

5.3. Inclusion Criteria

Participants must meet all of the following inclusion criteria to participate in this study:

1. Age ≥ 18 years
2. HIV infection
3. Sub-optimal adherence to ART (Less than “always” taking ART medication and/or VL >20 copies/mL);
4. Psychological distress (PHQ-4 score ≥ 2);
5. Access to a telephone or cell phone

5.4. Exclusion Criteria

Participants meeting any of the following criteria will be excluded from participating in this study:

1. Inability or unwillingness to give informed consent
2. Cognitive impairment
3. Non-English speaking

4. Enrollment in another ongoing behavioral research project
5. Prior formal training in MBSR or active practice of mindfulness, meditation, or related mind-body techniques in the past year
6. Severe hearing impairment not allowing phone delivery
7. Suicidal ideation
8. Psychosis (e.g., diagnosis of a severe and persistent mental disorder)
9. Planning to move out of the area within the study period
10. Health care provider (i.e. physician, nurse, or mental health professional) at the Immunology Clinic recommends patient should not be approached for the study

6. ENROLLMENT

6.1. Recruitment Processes

Participants will be recruited from patients receiving care at the Immunology Center at The Miriam Hospital. [name], a Co-Investigator on the project who is also a clinic treatment provider, will act as a liaison between the study and the clinic. The Immunology Center is an enthusiastic supporter of clinical research.

Study 4 will rely on four methods of recruitment: (1) patients from the clinic, using a patient database query and in person recruitment, (2) direct referral from clinic providers (e.g., research nurses, physicians, mental health professionals) at the Immunology Center followed up by in person recruitment, (3) recruitment letter, and (4) phone recruitment.

(1) Direct appeal to patients in person: The Immunology Center Database (ICDB) will be queried to identify all patients who have had a detectable HIV-1 Plasma viral load within the past 12 months, are 18 years of age or older, and have an upcoming appointment within the next 3 months. The PD will review the IC appointment list on a daily basis to assess which patients from the ICDB query are coming in for an appointment. The PD will review the eligibility with the participant's HIV provider. If considered eligible by the HIV provider, the PD will approach the patient at their scheduled appointment.

(2) Physician referral: The PD will share some eligibility criteria with clinic providers from the IC through the use of a flyer which can be emailed or hand delivered. The PD will ask for referrals from the clinic providers. The PD will check the IC appointment list to assess the patient's next clinic visit. The patient will be approached in person at their scheduled appointment.

(3) Direct appeal to patients by Letter: The Immunology Center Database (ICDB) will be queried to identify all patients who have had a detectable HIV-1 Plasma viral load within the past 12 months and are 18 years of age or older. The PD will review the eligibility with the participant's HIV provider. The PD will ask the HIV provider if contacting the participant via letter is appropriate. If the HIV provider provides permission the PD will mail the recruitment letter.

(4) Direct appeal to patients by phone: If no response is received within two week of mailing the letter (see #3), the PD will ask the HIV provider if contacting the participant via phone is appropriate. If the HIV provider provides permission for phone contact the PD will call the participant following the phone recruitment script.

If a participant is found ineligible or refuses to be screened and/or participate at any of above the four recruitment methods he or she will not be contacted again for the life of the study.

6.2. Screening and Consenting Procedures

For recruitment methods (1) and (2) the PD will meet individually with referred patients in a private room at the Immunology Center. For recruitment methods (3) and (4) the PD will screen the participant via telephone. The PD will summarize the study and its requirements and enquire whether the patient is still interested. If the patient is interested, the PD will explain the need to collect some preliminary information to determine whether he/she is eligible to participate. A screening script and screening instrument will be used to standardize this phase of screening. Patients meeting initial eligibility criteria will receive a thorough explanation of the study design, including what they will be expected to do if they join the study as well as detailed information regarding risks and benefits. All questions answered to the patient's satisfaction and understanding.

Once informed consent procedures are completed, the PD will complete screening assessments to confirm the participant's eligibility for the study (see 8.2 for a detailed description of screening assessments).

Participants who are eligible and agree to participate will proceed to the completion of all baseline measures, with the exception of baseline objective assessments of ART adherence.

Screen failures

Filemaker Pro will be used for tracking all participants for Study 4 who expressed interest in participating and were screened for eligibility. We will collect data from all individuals assessed for eligibility (i.e., individuals who consented but then resulted non-eligible at the completion of the screening process) so that we can provide a complete Consort diagram and description of the recruitment process both for publication purposes and as an indicator of future generalizability of the study. We estimate that 70% of screened participants will be eligible for this study.

Screening window

We will make every effort to minimize the time between the completion of all screening procedures and the beginning of the intervention in Study 4 (max, 8 weeks).

Randomization

After all baseline assessments have been completed, the PD will randomly assign participants (1:1 ratio) to the MT or AC condition using a randomization schedule generated by the study biostatistician, [name]. The schedule will be generated using a permuted block randomization procedure with small, random-sized blocks. The allocation table will be password protected and saved to the CBPM secure drive. The unit of randomization will be the individual patient. We do not anticipate contamination between MT and AC, as patients will likely have no chance to exchange experiences about the interventions and instructors delivering the MT intervention will be different from those delivering the AC intervention.

Participants will be given the option to pick up intervention materials in person after randomization occurs or to have the materials mailed to them. Intervention materials for the MT condition consist of a compact disc with audio recordings of the mindfulness instructor's voice as well as a box of raisins to be used during mindfulness sessions and daily practice. Scripts of these recordings are located in Appendix 1 of this protocol. The compact disc doesn't contain the name of the study nor any identifying information about the study or the participant. Intervention materials for the AC condition consist of a packet of material pertaining to the session topics (i.e. nutrition, sleep) that is available to the public on the internet. These materials were chosen from websites such as the Centers for Disease Control and the

American Heart Association. Intervention materials for both MT and AC condition do not mention HIV or HIV status.

6.3. Retention Plan

Patients will be asked to provide two different telephone numbers (home and mobile phone number) and an email address. Participants will be asked to provide contact information for two locators to be used in the event that contact is lost with the participant. Locators will not be given information about the nature of the research study. The study tracking system will identify participants due for a visit. We will send mail/email reminders or phone messages to remind patients of their follow-up appointments. Participants who wish to drop out of the study will be queried as to their reasons for doing so and every attempt will be made to address their concerns. In addition, we will provide monetary compensation to patients for their time and expenses. Participants will receive \$40 cash for the baseline assessment, \$40 cash for the post-intervention assessment, \$50 cash for the follow-up assessment and \$10 cash each for the pill count telephone calls (seven total) for a total of \$200.

If a participant does not complete all of the baseline procedures (including the two pill counts) within 60 days of enrollment, then he or she will be considered lost to follow-up.

If a participant does not complete two intervention weeks in a row he or she may be withdrawn from the intervention portion of the study per PD and PI discretion. These participants would still be contacted for pill count assessments and follow-up assessments.

7. DESIGN AND DRAFT PROCEDURES

This is a pilot, Phase 2, behavioral randomized controlled trial, which is primarily designed to determine the feasibility and patient acceptability of mindfulness training for improving adherence to ART and promoting safer sex practices among persons living with HIV (PLWH).

As a secondary purpose, we will obtain preliminary estimates of efficacy of MT on two clinically relevant outcomes (namely, actual adherence to ART and adoption of safer sexual practices) and the hypothesized mediators (i.e., mindfulness, depression, perceived stress, impulsivity).

7.1. Study Outcomes

Primary outcomes: feasibility and acceptability.

Feasibility: Key metrics will include the number of screened, eligible, consented and randomized participants; retention rates; session attendance; and individual mindfulness practice. We will consider either condition feasible under the following conditions:

- 1) If we achieve retention rates of 80% at the final follow-up visit
- 2) If patients attend at least 70% of the planned sessions
- 3) If patients report to have completed 70% of the assigned individual home practice exercises
- 4) Intervention session calls lasting approximately 20 minutes
- 5) Fewer than three rescheduled intervention calls

Acceptability: We will assess the following domains:

- 1) Participants' experience in the study (qualitative data collection)

- 2) Participants' ratings of the interventions on a satisfaction survey. The intervention will be considered acceptable if ≥80% of participants responds that they are at least somewhat satisfied with the intervention.

Secondary outcomes:

Preliminary estimates of effect size of mindfulness training vs. attention control on changes from baseline ART adherence, risky sex behaviors as well as on hypothesized mediators (i.e., mindfulness, depression, perceived stress, and impulsivity) will be assessed. We expect that the mindfulness training condition will achieve larger positive changes in ART adherence and risky sexual behaviors compared to the attention control condition.

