Please note that retention, attendance are feasibility outcomes; consequently dropouts, missing session, and missing self-reported practice will not be considered protocol deviations. This information will be collected and monitored (as aggregate data and without breaking the PI blind status).

Protocol amendments. Please also note that given the pilot nature of this study, we may need to amend the original protocol in response to feasibility issues (e.g., if we realize that our eligibility criteria are too strict, unnecessary and negatively affect recruitment). If needed, we will submit an amended protocol to NCCIH for approval in the following cases: any change that may affect patient safety (e.g., change in eligibility criteria; change in risk, regardless of whether risk is increased or decreased); any change that changes scientific intent or study design, or affects human subject protection; addition/deletion of a site; addition/deletion of key study personnel; change of institution for key study personnel; change in enrollment targets. Amendments will also be submitted to the IRB in accordance with IRB policies at TMH.

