12.2. Primary Outcomes: Feasibility and Acceptability

Because this is a pilot study, analyses are not powered to detect treatment effects nor to formally test mediation or moderation. Any formal statistical testing will be only exploratory.

Feasibility. To determine feasibility of conducting a RCT, we will calculate the percentage of individuals who were: eligible; consented; accepted randomization; and returned for the post-intervention and 3-month follow-up. Based on our recent trials (R01-MH068171), we expect $\geq 80\%$ of all patients to return for the 3-month follow-up and will conclude the intervention is feasible if the follow-up rate is at least 80%. To determine feasibility of the MT and AC interventions, we will calculate the percentage of individuals who attended their intervention sessions. Based on previous research, we predict that $\geq 70\%$ of those assigned to a MT will complete all intervention sessions.

Acceptability. To determine the acceptability of the interventions, we will calculate means for the satisfaction surveys, and inspect responses. The intervention will be considered acceptable if $\geq 80\%$ of participants respond that they are satisfied with the intervention. We will also collect metrics (e.g., duration of calls, number of cancelled sessions). We will construe as evidence of acceptability, patients completing all ≥ 7 sessions, with call durations averaging 20 minutes per call, and with fewer than 3 rescheduled sessions.

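### Section 7.1 judges each condition feasible on five criteria, but the only explicit feasibility decision sentence in 12.2 rests on follow-up alone; both sections use a 20-minute call benchmark for a 30-minute session

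*Combined protocol and SAP*

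**What the plan says.** Section 7.1 introduces the feasibility rule with "We will consider either condition feasible under the following conditions" and gives five numbered criteria. It does not say whether all five are needed.

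Section 12.2 has two parts on feasibility. The first concerns the feasibility of running a randomised trial, and ends by saying the team "will conclude the intervention is feasible if the follow-up rate is at least 80" per cent. The second reads "To determine feasibility of the MT and AC interventions, we will calculate the percentage of individuals who attended their intervention sessions". It sets no pass mark, only a prediction that at least 70% "of those assigned to a MT will complete all intervention sessions". Under acceptability, 12.2 then counts as evidence "patients completing all ≥ 7 sessions, with call durations averaging 20 minutes per call, and with fewer than 3 rescheduled sessions".

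Two other sections bear on this. Section 11.5 states that "retention, attendance are feasibility outcomes; consequently dropouts, missing session, and missing self-reported practice will not be considered protocol deviations". Section 6.3 says that a participant who misses two consecutive intervention weeks "he or she may be withdrawn from the intervention portion of the study per PD and PI discretion", and adds: "These participants would still be contacted for pill count assessments and follow-up assessments".

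On call length, 7.1 and 12.2 both use about 20 minutes. Section 7.3 and the schedules in Appendices 1 and 2 plan 30 minutes per session in both conditions.

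**The concern.** Two stated decision rules for one primary outcome can return opposite verdicts, and nothing says which governs. 12.2 does not refer back to 7.1.

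The criteria that drop out of the 12.2 sentence matter to the rationale. Section 2.2 gives poor class attendance and high attrition as two separate reasons why earlier group-based studies may have under-dosed participants, and lists delivery of an adequate dose among the purposes of this research. The 12.2 sentence addresses attrition only. Because 11.5 takes missed sessions and missing practice reports out of the protocol deviations on the ground that they are feasibility outcomes, the feasibility rule is where a shortfall should count.

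The call-length benchmark raises a different problem. Under 4.7, instructors check the duration of each session against the script. A call could match its script and still miss the feasibility figure.

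**Working it through.** **1. Planned session length (the plan's own figure).** Inputs are the minutes printed in the Appendix 1 and 2 outlines.
- MT sessions 1, 3, 5, 6, 7: 10 + 10 + 10 = 30. Sessions 2 and 4: 10 + 10 + 5 + 5 = 30. Session 8: 10 + 15 + 5 = 30.
- AC sessions 1 to 8: 5 + 10 + 10 + 5 = 30.

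All 16 outlines reproduce the 30 minutes. A 20-minute call is 20/30 = 67% of that, or 8 × 20 = 160 of 8 × 30 = 240 minutes over the course.

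**2. The two sections side by side.**

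| Item | 7.1 | 12.2 |
|---|---|---|
| Retention | 80%, feasibility | 80%, the feasibility conclusion |
| Attendance | at least 70% of sessions, feasibility | percentage calculated, no pass mark; MT prediction only |
| Home practice | 70%, feasibility | absent |
| Call length | about 20 min, feasibility | average 20 min, acceptability |
| Rescheduling | fewer than 3, feasibility | fewer than 3, acceptability |
| Satisfaction | 80% somewhat satisfied or better | 80% satisfied |

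**3. Attendance takes three forms.** 70% of 8 sessions is 5.6, so one patient needs 6 of 8 (75%) to reach the 7.1 figure. The 12.2 prediction concerns all 8 (100%). The 12.2 acceptability sentence combines all with 7 or more (7/8 = 87.5%). If every patient in an arm attended 6 of 8, attendance would be 25 × 6 = 150 of 200 (75%), which meets 7.1, while 0/25 completed every session.

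**4. Can the verdicts differ?** Planned sessions per arm: 25 × 8 = 200; 70% is 140. Follow-up mark: 0.80 × 25 = 20.
- 20/25 retained, with an average of four sessions each: 25 × 4 = 100/200 = 50%. Passes the 12.2 sentence, misses 7.1.
- Under the 6.3 provision: 11 withdrawn from the intervention after two sessions, 14 attending all eight, all 25 seen at follow-up. Attendance is 11 × 2 + 14 × 8 = 22 + 112 = 134/200 = 67%, with 100% retention. With 10 withdrawn it is 10 × 2 + 15 × 8 = 140/200, exactly 70%.

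These are illustrations, not forecasts. The second needs 11/25 = 44% withdrawn from the intervention and complete follow-up.

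**5. Does the level of summary matter?** Fifteen patients at 6 sessions and ten at 5 give 90 + 50 = 140/200 = 70%. Only the fifteen are individually at 70% or more (6/8 = 75%; 5/8 = 62.5%), so the share of patients reaching the mark is 15/25 = 60%. An arm total and a share of patients are therefore different criteria. 7.1 does not say which it means; 12.2 speaks of a percentage of individuals.

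**The case against.** The best defence is that 12.2 is incomplete more than contradictory. Its two parts separate trial conduct from the interventions, the 80% sentence closes the first, the retention figure is the same in both sections, and nothing says 12.2 replaces 7.1. Much of this stands: the sentence may well have been meant for trial conduct. It does not remove the gap, because the sentence's subject is the intervention, and the part devoted to the interventions draws no conclusion. On either reading, 12.2 does not carry out the 7.1 rule.

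Four stronger readings are tempting, and the documents do not support them.
- A reader might infer that 12.2 drops attendance. It does not: attendance is still calculated, 11.5 names it a feasibility outcome, and Table 8.2 collects attendance and home practice regardless.
- A reader might infer that 12.2 holds no other decision rule. It has one for acceptability, based on 80% satisfied; the gap concerns feasibility.
- A reader might infer that fully delivered 30-minute calls fail. That follows only if 20 minutes is a target or ceiling. A floor is plausible but unstated.
- A reader might cite the 2.2 statement that confirming an adequate dose is key. In context it concerns the hypotheses of the future trial, not this pilot's verdict.

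It is also fair that 12.2 calls any formal testing exploratory, that 12.6 sets the sample size on practical grounds, and that no progression gate is stated.

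**Conclusion.** The point holds as a mismatch between two sections on a primary outcome. Section 7.1 requires more than retention; the only feasibility conclusion written into 12.2 requires retention alone, and 6.3 means retention cannot stand in for attendance. The gap can be wide: an arm at 50% attendance could be reported feasible under one section and not under the other. That example assumes 25 patients per arm, eight planned sessions, attendance taken as an arm total, and 7.1 read as requiring its attendance criterion.

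The call-length point is narrower: the benchmark is two-thirds of the planned session and lacks a direction, so its meaning has to be stated.

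The consequence is confined to the reported feasibility verdict that will inform the later trial. It should be fixed, but it does not threaten the conduct of the pilot or its exploratory estimates.

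**What to change.** Before outcome data are reviewed:

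- (a) Replace the 12.2 feasibility decision sentence with the 7.1 per-condition criteria, and state that all are required or name those that are.
- (b) Choose one level for attendance and home practice, either the share of patients reaching 70% or the arm total over all randomised. Use it in both sections and report the other descriptively. Section 8.4 collects practice reports during sessions, so also say how practice left unreported because of a missed session is counted.
- (c) Put call length and rescheduling in one domain, the same in both sections.
- (d) Use one satisfaction wording, and name the scores on the 0 to 6 scale in 8.4 that meet it.
- (e) Reconcile the 20-minute criterion with the 30-minute session and state its direction, so that full delivery cannot count against feasibility. The session length itself is for the sponsor to settle.

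The cost is protocol and SAP wording. No new data are needed.
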